#### **Study design:**

This is a 4 week open-label, non-blinded, non randomized study in patients with fecal incontinence.

The study will consist of two periods of two weeks:

- First two weeks - control period: Patients will be asked to continue his / her normal life and to answer to validated questionnaires of fecal incontinence, quality of life and to fill a stool diary.
  - The first week will be considered as the baseline period
  - The second week as the control period.

- Second two weeks - treatment period: Patients will be provided with the device, and ask to answer to the same questionnaires, stool diary and an additional usability questionnaire.

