### **Exclusion criteria:**

- Advanced full thickness rectal prolapse.
- Injured, inflamed or any significant disease in the peri-anal skin.
- Allergy to any component of the device, either known or developed during testing in the screening visit (see below).
- Moderate to severe proctitis of any etiology.

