### **Outcome variables:**

Primary outcomes:

- Any improvement in any of the domain explored by the Fecal Incontinence quality of life questionnaire[14].

Secondary outcomes:

-

- A 50% reduction in the number of episodes of FI or days per week, evaluated with the bowel diary and the weekly Wexner questionnaire.
- Any improvement in Wexner score, both total score and any of its components.
- Any improvement in quality of life score, and in any of its component.
- Usability score
- General satisfaction using a VAS score.
- Willingness of the patient to continue using the anal tape after the study.

Safety outcome:

- Any adverse effect that can be related to the device.

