### **Number of patients:**

In this study each patient will be his own control before and after the intervention. We expected minimal change (if any) during the control period. We calculated that 20 patients in each group are required to have a 80% chance of detecting, (with a significant 5% level), an increase in 5 points in the quality of life questionnaire from 20% in the control period to 60% in the treatment period.

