### **Study procedures:**

The study includes 3 office visits:

- Screening day 0:
  - Obtain informed consent for participation.
  - Personal information and demography: Age, medications, medical history, obstetric history (e.g. number of vaginal deliveries, obstetric anal sphincter injury) etc.
  - Obtain detailed FI related history:
    - Possible etiology
    - Review sigmoidoscopy and manometric data.
    - Type of FI:
      - Stool consistency
        - Gas
        - Liquid
        - Solid
      - Urge incontinence
      - Passive incontinence
  - Physical examination including digital rectal examination.
  - Overview of inclusion and exclusion criteria.
  - Obtain informed consent
  - Explain the use of the "anal tape"

- Apply the "anal tape" to the arm or leg for 30 minutes in order to examine unexpected skin reaction to the device.
  - Provide the patient with the questionnaires:
    - To fill immediately:
      - Quality of life
      - Wexner
    - To fill in day 7 of study
      - Quality of life
      - Wexner
    - Bowel / stool diary
  - Insert all data into the database.
- Follow up day 14:
    - Retrieve questionnaires from day 7 and stool diary.
    - Explain again the use of the "Anal Tape"
    - Provide the patient with 28 (two for every day of the intervention period) single use "Anal Tapes".
    - Provide the patient with additional questionnaires:
      - To fill immediately:
        - Quality of life
        - Wexner
      - To fill in day 21 of study
        - Quality of life
        - Wexner
      - Bowel / stool diary
    - Insert all data into the database.
- Follow up day 28 and end of study:
    - Retrieve questionnaires from day 21 and stool diary.
    - Provide the patient with additional questionnaires:
      - To fill immediately:
        - Quality of life
        - Wexner
        - Usability score
    - Ask the patient about general satisfaction using a VAS score.
    - Ask the patient about willingness to continue using the anal tape after the study (yes or no answer).
    - Insert all data into the database.

Anorectal manometry:

- If there is clinical indication to perform anorectal manometry (according to one of the investigators), a new anorectal manometry will be required as part of the regular clinical evaluation, but in these cases we will measure anal pressure with and without the "anal tape" in situ.
  - We expect that up to 10 patients will require this additional evaluation.

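### The only safety outcome counts device-related effects, so perianal skin events have no control-period rate to be read against

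*Combined protocol and SAP*

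**What the plan says.** The *Aims of study* section names safety alongside efficacy. Under *Outcome variables*, the one safety outcome is "Any adverse effect that can be related to the device". No section says who decides on relatedness, by what criteria, or over what time window.

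The design is a single-group before-and-after comparison: "This is a 4 week open-label, non-blinded, non randomized study in patients with fecal incontinence". The periods are "First two weeks - control period: Patients will be asked to continue his / her normal life" and then "Second two weeks - treatment period: Patients will be provided with the device". The *Number of patients* section gives the logic: "In this study each patient will be his own control before and after the intervention".

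*Study procedures* issues the tapes at the day 14 visit. Before that, the only contact with the device is a 30-minute application to the arm or leg at screening. Bowel data are gathered in both periods: at day 14, "Retrieve questionnaires from day 7 and stool diary", and at day 28, "Retrieve questionnaires from day 21 and stool diary". The quality of life and Wexner questionnaires are also completed in both periods. A physical examination is listed at screening only. Neither the day 14 nor the day 28 visit lists an adverse-event question or a skin check.

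*Exclusion criteria* removes patients with "Injured, inflamed or any significant disease in the peri-anal skin". The *Statistical Analysis Plan* names no safety analysis.

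**The concern.** The likely harms of an adhesive worn around the anus overlap with what leaking stool does to the same skin. The *Introduction* itself lists skin care as part of managing fecal incontinence. A sore perianal area in week 3 may come from the tape, from leakage, or from both. Within one patient, the natural evidence is whether the same complaint was present in weeks 1-2, when no tape was worn. The plan uses that comparison for quality of life, for the Wexner score and for episodes of incontinence. The wording of the safety outcome rules it out for adverse events.

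The study would end with a count of events that someone thought could be due to the tape, and no device-free count from the same patients beside it. Such a count says little about safety in either direction: a high one may be mostly background, and a low one may reflect strict attribution.

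**Working it through.** **1. What each period can contribute**

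| Item | Weeks 1-2, no tape | Weeks 3-4, tape |
|---|---|---|
| Quality of life, Wexner | Yes (days 0, 7, 14) | Yes (days 21, 28) |
| Stool diary | Yes (returned day 14) | Yes (returned day 28) |
| Perianal skin | Screened at day 0; no later check listed | No check listed |
| Adverse events under the outcome definition | None possible, except from the arm or leg test | Only those that can be related to the tape |
| Adverse-event question at the closing visit | Not listed | Not listed |

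The fourth row follows from two statements taken together: relatedness is required for counting, and no tape is in use before day 14. An allergy seen in the arm or leg test is an exclusion criterion, so it removes a patient and supplies no control-period observation.

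**2. Would adding a question at day 28 be enough?** No. Under the present definition, it would produce an attributed count for weeks 3-4 and still nothing for weeks 1-2. The missing collection step and the missing comparator are separate gaps. Both need closing.

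**3. Does the entry exclusion supply the comparator?** Only coarsely. It establishes that there was no significant perianal skin disease at day 0. Patients then continue as usual for two weeks before receiving the tape. A skin problem that begins in that time is recorded nowhere and can later be read as tape injury.

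**4. How often would background complaints arise?** The plan gives no safety figure to reproduce. Its sample size concerns quality of life response, 20% against 60%. The two-sided unpooled formula gives (1.960 + 0.842)² × (0.2×0.8 + 0.6×0.4) / 0.4² = 19.6, rounded up to 20, so that figure reproduces. It has no bearing on safety, but it sets n. I take n = 20 in all, because there is one group.

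The documents give no background rate p of a perianal complaint over two weeks, so a range is assumed. With patients independent and a tape that does nothing, P(at least one complaint in weeks 3-4) = 1 − (1 − p)^20:

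| Assumed p | Expected patients, 20p | P(at least one) |
|---|---|---|
| 1% | 0.2 | 18% |
| 5% | 1 | 64% |
| 10% | 2 | 88% |
| 15% | 3 | 96% |

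Each such event could be counted or left out, and the planned data hold no device-free rate to help decide.

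**5. What would a control-period count add?** Let b be the proportion with an event in weeks 1-2 and t the proportion in weeks 3-4, both assumed. Write p01 for the share of patients with an event in weeks 1-2 only and p10 = t − b + p01 for the share with one in weeks 3-4 only. Two cases were taken: events independent between periods, p01 = b(1 − t), and every patient with an event in weeks 1-2 also having one in weeks 3-4, p01 = 0. Exact two-sided 5% McNemar power with n = 20:

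| b against t | Power over the two cases |
|---|---|
| 10% against 20% | 1% to 4% |
| 10% against 30% | 19% to 20% |
| 10% against 40% | 44% to 58% |

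Even zero events in 20 patients leaves a one-sided 95% upper limit of 1 − 0.05^(1/20) = 13.9%. The comparison helps in interpreting individual events. It is not a test of safety.

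**The case against.** The best defence has four parts.

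First, the plan does compare symptoms between periods. The diary and the Wexner questionnaire cover both, so worsening incontinence on the tape can be seen within patients. This stands. A reader might infer that bowel symptoms as a whole lack a comparator; the documents do not support that. The gap is confined to perianal skin events and to symptoms those instruments miss. The diary's items are not listed, so the exact edge of the gap is unknown.

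Second, perianal skin is screened at entry. This stands as a day-0 baseline only, since no repeat check is listed.

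Third, the wording is inclusive: an effect that can be related would naturally take in possibly related events, and a new skin complaint under the tape would plausibly qualify. This also stands. A reader might infer that the developers will judge relatedness and will under-count. The authors do say that they developed the tape, and the study is open-label, but they also state that they have no commercial interest, and no assessor is named. Attribution could shrink the count and background symptoms could swell it. The documents do not establish a net direction.

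Fourth, in a 20-patient, fixed-order, open-label study, a side-by-side comparison proves little. This is correct and limits the benefit of the change. It does not rescue the present definition, which yields a count without a comparator even if followed exactly.

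**Conclusion.** The point holds for adverse events outside the diary and Wexner, above all perianal skin events. Making relatedness an entry condition, with tapes issued at day 14, leaves a stated aim of the study without the own-control comparison on which the design rests. That conclusion comes from the text and needs no assumed rate.

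The size of the problem cannot be fixed from the documents. Under assumed background rates of 1% to 15% per two weeks, the chance of at least one unrelated complaint in weeks 3-4 runs from 18% to 96%. A reader might want a definite number of miscounted patients; any such number would simply be the assumed rate multiplied by 20, and the entry exclusion may make the true rate low. A reader might also infer that closing the gap would let the study call the tape safe or unsafe. It would not, given the sample size, the fixed order and the lack of blinding.

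The change is worth making. It leaves the sample size and the efficacy analysis untouched.

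**What to change.** - Redefine the safety outcome as all adverse events, plus a short fixed list of perianal symptoms, regardless of cause.
- Ask about them in the same words at two existing visits: day 14 for weeks 1-2 and day 28 for weeks 3-4. Add both questions to *Study procedures*.
- Record device-relatedness as a separate field, and state who assesses it and by what criteria.
- In the *Statistical Analysis Plan*, report both periods side by side, with the number of patients whose events were new or worse in weeks 3-4 than in weeks 1-2. Label this descriptive.

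The cost is a few extra questions at visits already planned, a longer event listing, and a crude count that will look less favourable because it includes background complaints. No extra patients or visits are needed.

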### **Number of patients:**

In this study each patient will be his own control before and after the intervention. We expected minimal change (if any) during the control period. We calculated that 20 patients in each group are required to have a 80% chance of detecting, (with a significant 5% level), an increase in 5 points in the quality of life questionnaire from 20% in the control period to 60% in the treatment period.

### **Study procedures:**

The study includes 3 office visits:

- Screening day 0:
  - Obtain informed consent for participation.
  - Personal information and demography: Age, medications, medical history, obstetric history (e.g. number of vaginal deliveries, obstetric anal sphincter injury) etc.
  - Obtain detailed FI related history:
    - Possible etiology
    - Review sigmoidoscopy and manometric data.
    - Type of FI:
      - Stool consistency
        - Gas
        - Liquid
        - Solid
      - Urge incontinence
      - Passive incontinence
  - Physical examination including digital rectal examination.
  - Overview of inclusion and exclusion criteria.
  - Obtain informed consent
  - Explain the use of the "anal tape"

- Apply the "anal tape" to the arm or leg for 30 minutes in order to examine unexpected skin reaction to the device.
  - Provide the patient with the questionnaires:
    - To fill immediately:
      - Quality of life
      - Wexner
    - To fill in day 7 of study
      - Quality of life
      - Wexner
    - Bowel / stool diary
  - Insert all data into the database.
- Follow up day 14:
    - Retrieve questionnaires from day 7 and stool diary.
    - Explain again the use of the "Anal Tape"
    - Provide the patient with 28 (two for every day of the intervention period) single use "Anal Tapes".
    - Provide the patient with additional questionnaires:
      - To fill immediately:
        - Quality of life
        - Wexner
      - To fill in day 21 of study
        - Quality of life
        - Wexner
      - Bowel / stool diary
    - Insert all data into the database.
- Follow up day 28 and end of study:
    - Retrieve questionnaires from day 21 and stool diary.
    - Provide the patient with additional questionnaires:
      - To fill immediately:
        - Quality of life
        - Wexner
        - Usability score
    - Ask the patient about general satisfaction using a VAS score.
    - Ask the patient about willingness to continue using the anal tape after the study (yes or no answer).
    - Insert all data into the database.

Anorectal manometry:

- If there is clinical indication to perform anorectal manometry (according to one of the investigators), a new anorectal manometry will be required as part of the regular clinical evaluation, but in these cases we will measure anal pressure with and without the "anal tape" in situ.
  - We expect that up to 10 patients will require this additional evaluation.

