Minimally invasive procedures such as injection of bulking agents to the anal sphincter and muscle augmentation with radiofrequency ablation (SECCA) as well as surgical interventions and sacral nerve stimulation may be of use to some patients but are complex, expensive and associated with adverse effects.

Consequently local mechanical devices, that can be applied externally are very attractive, some of them are already commercially available.

We developed an "anal tape" using a commercially available elastic band with a special adhesive that is approved for use in the skin. This adhesive band is available worldwide and is used by numerous people, especially athletes. The band can be fashioned in any form and taped to any area of the body with a healthy skin and is for single use. Thus a square of the band with a small opening in the center can be applied to the skin surrounding the anus providing support and additional pressure forces to the anal sphincter.

This study will explore the efficacy and safety of this device in patients with FI, importantly the tape is commercially available; thus we have no commercial interest in the success of the device.

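### At day 28, satisfaction and willingness to continue are to be asked of the patient without saying by whom or how, so courtesy answers may inflate these two descriptive secondary outcomes

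*Combined protocol and SAP*

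**What the plan says.** The day-28 entry under Study procedures collects patient-reported data in two ways. Under the line "Provide the patient with additional questionnaires" it lists quality of life, Wexner and the usability score, which the patient completes at the visit. Two further items stand outside that list, on lines of their own: "Ask the patient about general satisfaction using a VAS score" and "Ask the patient about willingness to continue using the anal tape after the study (yes or no answer"). In the visit schedule this form of words is used only for these two items. Nothing states who puts the questions, whether the patient marks the VAS unaided, or whether anyone outside the developing team collects the answers.

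Outcome variables lists six secondary outcomes. Two of them are these items: satisfaction ("General satisfaction using a VAS score") and willingness to go on using the tape.

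Two other sections bear on the point. The Study design section states: "This is a 4 week open-label, non-blinded, non randomized study in patients with fecal incontinence". The Introduction's account of the device begins "We developed an", so the protocol's authors are its developers. The same section adds a disclaimer: "thus we have no commercial interest in the success of the device".

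**The concern.** A patient who is asked in person, at the closing visit, whether they liked a device and would keep using it may give a kinder answer than they would on paper. The pull is stronger if the person asking helped to develop the device, and the protocol does nothing to prevent that.

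These items also lack a partial safeguard that other outcomes have. Quality of life and Wexner are recorded on days 0, 7, 14, 21 and 28, so a patient's constant habit of answering favourably partly cancels in the within-patient comparison. Satisfaction and willingness are recorded only on day 28. They will be reported as levels, and any favourable lean enters those levels in full. An answer already given face to face cannot be corrected in the analysis.

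What is at stake is how far the satisfaction and willingness results can be trusted as descriptions of acceptability. The efficacy conclusion is not at stake.

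**Working it through.** **1. How each day-28 item is collected**

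| Day-28 item | Route in Study procedures | Control-period value |
|---|---|---|
| Quality of life | Form, completed at the visit | Yes |
| Wexner | Form, completed at the visit | Yes |
| Usability score | Form, completed at the visit | No |
| Satisfaction (VAS) | Asked; who asks and who marks the scale not stated | No |
| Willingness (yes/no) | Asked; who asks not stated | No |

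Satisfaction and willingness are the only items that are both asked and without a control-period value.

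**2. The plan's own figure**

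The point needs only a denominator. Number of patients gives 20 per group, for 20% against 60% at the 5% level with 80% power. The unpooled normal formula reproduces it:

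n = (1.960 + 0.842)² × (0.2×0.8 + 0.6×0.4) / 0.4² = 7.85 × 0.40 / 0.16 = 19.6, rounded up to 20.

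Each patient is their own control, so I take 20 as the number answering on day 28. One patient is then 1/20 = 5 percentage points.

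**3. Possible size for willingness**

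The documents give neither a true willingness rate nor a rate of courtesy answers, so both are assumptions. Let q be the true proportion willing and c the share of unwilling patients who nevertheless say yes. Then:

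- observed proportion = q + c(1 − q)
- inflation = c(1 − q)
- extra yes answers = 20 × c(1 − q)

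Example with q = 0.50 and c = 0.20: observed = 0.50 + 0.20 × 0.50 = 0.60, which is 10 points or 2 patients too high.

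| True willingness q | c = 0 | c = 10% | c = 20% | c = 30% |
|---|---|---|---|---|
| 30% | 30% (0) | 37% (+1.4) | 44% (+2.8) | 51% (+4.2) |
| 50% | 50% (0) | 55% (+1) | 60% (+2) | 65% (+3) |
| 70% | 70% (0) | 73% (+0.6) | 76% (+1.2) | 79% (+1.8) |

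Cells show the observed rate, with the expected number of extra yes answers among 20 patients. The percentage-point shift does not depend on n.

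**4. Set against sampling error**

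An observed 12/20 (60%) has an exact (Clopper-Pearson) 95% interval of 36.1% to 80.9%, a half-width of (80.9 − 36.1)/2 = 22.4 points. The 5–15 point shifts at q = 50% are smaller than that. But they all run one way, and the interval makes no allowance for them.

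**5. Satisfaction**

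No size can be given. The documents state neither the length nor the anchors of the VAS, and they do not show that an interviewer records it.

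**The case against.** Much of the case on the other side stands.

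- **Who asks.** A reader might infer that the developers themselves put the questions. The protocol identifies its authors as developers but does not say who conducts the day-28 visit. It also disclaims commercial interest. That does not remove a patient's wish to please, but a fair account must include it.
- **The VAS.** A VAS is ordinarily marked by the respondent, and the wording is compatible with handing the patient a line to mark. A reader might infer that both items are interviewer-administered; only willingness reads plainly as a spoken question.
- **The contrast with the forms.** The other day-28 questionnaires are also completed at the visit, with no anonymity described. In an open-label, single-group study every patient-reported outcome, including the primary, is open to response bias. Usability has no control-period value either. Repeated measurement cancels only a constant habit of answering, not courtesy that begins when the device is handed over. So the difference between these two items and the rest is one of degree.
- **Occurrence and size.** A reader might infer that inflation will occur, or construct a stark example such as 12/20 becoming 16/20. That example requires four of the eight unwilling patients, or half, to misreport. Nothing in the documents supports that rate, or any rate above zero.
- **Consequence.** Neither item is primary, has a success threshold or drives the sample size. The SAP's tests compare the control and intervention periods, so they cannot be applied to items recorded once.

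Three things survive these objections: the route of collection differs, it is unspecified where it matters most, and a form that would remove the difference is already in use at the same visit.

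**Conclusion.** The concern holds as a minor, inexpensive improvement. Satisfaction and willingness are to be asked of the patient by an unstated person and route, in an open-label study of a device its authors developed, with no control-period value to offset a favourable lean. Courtesy answers may inflate both. Willingness is the clearer case; for satisfaction the concern depends on how the VAS is completed, which the protocol does not say.

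The size is unknown. Assuming 50% true willingness, 20 respondents and courtesy answers from 10–30% of the unwilling, the reported rate would be 5–15 points too high. The shift would be larger if true willingness were lower, smaller if it were higher, and zero if nobody answered out of courtesy. The documents do not support reading this as demonstrated bias, or as a threat to the primary outcome or the sample size.

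**What to change.** In Study procedures, day 28, delete the two lines that have the patient asked. Add both items to the self-completed form, directly after the usability score: the satisfaction VAS, marked by the patient, and the yes/no willingness item. Add one sentence saying that the patient completes this form without staff questioning and before any discussion of results.

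The change needs two form lines and no extra visit, staff or patients. The downside is an occasional blank item, so report the number of blanks beside each result. Returning the form in a sealed envelope is optional; completing it without being questioned provides most of the benefit.
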